# 4.3.2 Safety and Tolerability

The assessment of safety will be based on the incidence of adverse events (AEs), serious adverse events (SAEs), adverse events leading to discontinuation, adverse events leading to dose modification, select adverse events (select AEs) for EU Submission, immune-mediated AEs (IMAEs) for US Submission, other events of special interest (OEOSI), and deaths. The use of immune modulating concomitant medication will be also summarized. In addition clinical laboratory tests, and immunogenicity (i.e. development of anti-drug antibody) will be analyzed.

#### 4.3.3 Pharmacokinetics

PK will be determined from serum concentrations of nivolumab in combination with ipilimumab. Samples will be collected to characterize pharmacokinetics of nivolumab in combination with ipilimumab and to explore exposure-safety and exposure-efficacy relationships.

# 4.3.4 Immunogenicity

Serum samples collected for immunogenicity will be assessed for nivolumab and ipilimumab antidrug-antibodies (ADA) and characterization of neutralizing antibodies. The immunogenicity data will be used to determine immune response rates and relationship of ADA with clinical safety and efficacy.

#### 4.3.5 EuroQoL EQ-5D-3L

Subjects' reports of general health status will be assessed using the EuroQoL Group's EQ-5D-3L. EQ-5D-3L essentially has 2 components: the descriptive system and the visual analogue scale (VAS).

The instrument's descriptive system consists of 5 dimensions: mobility, self-care, usual activities, pain/discomfort, and anxiety/depression. Each dimension has 3 levels, reflecting "no health problems," "moderate health problems," and "extreme health problems." A dimension for which there are no problems is said to be at level 1, while a dimension for which there are extreme problems is said to be at level 3. Thus, the vectors 11111 and 33333 represent the best health state and the worst health state, respectively, described by the EQ-5D-3L. Altogether, the instrument describes  $3^5 = 243$  health states. Empirically derived weights can be applied to an individual's responses to the EQ-5D-3L descriptive system to generate an index measuring the value to society of his or her current health. Such preference-weighting systems have been developed for the UK, US, Spain, Germany, and numerous other populations. For this study, EQ-5D-3L utility index values will be computed using a scoring algorithm based on the United Kingdom Time-Trade-Off (UK TTO) value set.

In addition, the EQ-5D-3L includes a VAS, which allows respondents to rate their own current health on a 101-point scale ranging from 0="worst imaginable" health to 100="best imaginable" health state.

A change from baseline of 0.08 for the EQ-5D-3L utility index score and of 7 for the EQ-5D-3L VAS are considered minimally important differences for the EQ-5D-3L.

All questionnaires completed at baseline and on-study will be assigned to a time-point according to the windowing criteria in Table 4.3.5-1 and included in the analysis. In case a subject has two on-study assessments within the same window, the assessment closest to the time-point will be used. And, in the case of two assessments at a similar distance to the time-point, the latest one will be chosen. In the event where the subject has no assessment at all in a specific window, the observation will be treated as missing for that time-point.

Table 4.3.5-1: Time Windows for EQ-5D and FACT-HN (FHNSI-10)

Nominal Time-Point	Time Window
Week 1 (Baseline)	≤ Date of first dose of study therapy
On-Treatment: (until last dose date)	
Week 7 (Day 43)	Day 2 - ≤ Day 64
Week 13 (Day 85)	Day 65 - ≤ Day 106
Week 19 (Day 127)	Day 107 - ≤ Day 148
Every 6 weeks thereafter while on treatment	Nominal Day (+ 21 days / - 20 days, inclusive)
Follow-up Visits 1 and 2	
Follow-up 1	If assessment is post last dose and within 76 days of last dose (if date of discontinuation is within 35 day after last dose)
	If assessment is post last dose and within 45 days of date of discontinuation (if date of discontinuation is greater than 35 days after last dose)
Follow-up 2	If assessment is post 76 days of last dose and within 173 days of last dose (if date of discontinuation is within 35 day after last dose)
	If assessment is post 45 days of date of discontinuation and within 137 days of date of discontinuation (if date of discontinuation is greater than 35 days after last dose)
Survival Follow-up Visit	
Survival Follow-up Visit 1	If 173 < assessment date - last dose date ≤ 173 + 90 (if date of discontinuation is within 35 days after last dose)
	If $137 <$ assessment date - date of discontinuation $\le 137 + 90$ (if date of discontinuation is greater than 35 days after last dose
Survival Follow-up Visit i	If $173 + (i-1) * 90 <$ assessment date - last dose date $\le 173 + i * 90$ (if date of discontinuation is within 35 days after last dose)
	If $137 + (i-1) * 90 <$ assessment date - date of discontinuation $\leq 137 + i * 90$ (if date of discontinuation is greater than 35 days after last dose

Table 4.3.5-1: Time Windows for EQ-5D and FACT-HN (FHNSI-10)

Nominal Time-Point		Time Window	

#### 4.3.6 FACT-H&N

The FACT-H&N questionnaire will be used to assess the effects of disease symptoms on functioning and well-being. As a generic cancer-related core, the FACT-H&N includes the 27-item FACT-General (FACT-G) to assess physical well-being (PWB; seven items), social/family well-being (SWB; seven items), emotional well-being (EWB; six items), and functional well-being (FWB; seven items). The FACT-H&N includes a 12-item disease-specific Head and Neck Cancer (HNC) subscale that assesses concerns related to vocalization, communication, breathing, eating, swallowing, appearance, and bother due to adverse events. Ten items included in the PWB, EWB, FWB, and HNC subscales contribute to the scoring of the FHNSI-10, which can be used to provide a targeted assessment of the effects of head and neck cancer symptoms. Each FACT-H&N item is rated on a five-point scale ranging from 0 (not at all) to 4 (very much). Scores for the PWB, FWB, SWB, and EWB subscales can be combined to produce a FACT-G total score, which provides an overall indicant of generic quality of life, while the FACT-G and HNC subscale scores can be combined to produce a total score for the FACT-H&N, which provides a composite measure of general and targeted quality of life. A variant of the total score that is often more sensitive to physical and functional outcomes, the Trial Outcome Index (TOI), can be derived by summing scores for the PWB, FWB, and HNC subscales. All scores are scaled so that higher values indicate better functioning as well as lower symptom burden.

The analysis window is the same as presented in Table 4.3.5-1.

#### 4.3.7 Time to Disease-related Symptom Deterioration

Time to disease-related symptom deterioration (TTSD) is defined as the time from randomization to a clinically meaningful decline from baseline FHNSI-10 score (worsening from baseline  $\geq 3$  points).

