8.3.3 Exploratory Endpoint(s)

Overall survival (OS) in randomized participants with tumor cell PD-L1 < 1%, or PD-L1 CPS of < 20, or tumor inflammation score measured as GEP \geq 10, or tumor mutation burden (TMB) \geq 7 is defined the same way as for the primary endpoints.

PFS, ORR, and DOR in randomized participants with tumor cell PD-L1 < 1%, or CPS of <20, or tumor inflammation score measured as GEP \geq 10, or tumor mutation burden (TMB) \geq 7 is defined the same way as for the secondary endpoints.

ORR and DOR in subpopulation based on selected biomarkers are defined the same way as in the secondary endpoints. Time to Objective Response (TTR) is defined as the time from randomization to the first documented response (CR or PR).

Safety and tolerability will be measured by the incidence of deaths, adverse events, serious adverse events, adverse events leading to discontinuation, immune-mediated adverse events, select adverse events, adverse events leading to dose delay, and specific laboratory abnormalities (worst grade) in each treatment group. Toxicities will be graded using the National Cancer Institute (NCI) Common Terminology Criteria for Adverse Events (CTCAE) version 4.0.

Tumor cell PD-L1 expression is defined as the percent of tumor cell membrane staining in a minimum of 100 evaluable tumor cells per validated Dako PD-L1 IHC assay. Participant's PD-L1 expression status using \geq 1% expression level will be determined prior to randomization:

- Tumor cell PD-L1 expressing ($\geq 1\%$ tumor cell membrane staining in a minimum of a hundred evaluable tumor cells)
- Tumor cell PD-L1 non-expressing ($< 1\%$ tumor cell membrane staining in a minimum of a hundred evaluable tumor cells)
- Tumor cell PD-L1 non-evaluable

Time to symptom deterioration (TTSD) is defined as the time from randomization to a clinically meaningful decline from baseline in the FHNSI-10 score. A clinically meaningful decline will be defined as a reduction of FHNSI-10 score ≥ 3 points.⁵⁶ Subjects who die without a reported deterioration will be considered to have deteriorated on the date of their death. Those who neither deteriorate nor die will be censored at the time of their last FHNSI-10 assessment.

Serum concentration will be used to characterize the PK of nivolumab and ipilimumab using a population PK approach.

Other exploratory endpoints are discussed in detail in the statistical analysis plan

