- The proportion (N) of participants with symptomatic deterioration, defined as a clinically meaningful decline in score (worsening from baseline ≥ 3 points) or death, will be summarized at each assessment time point (ie, first, second, third, etc. survival follow-up visit recognizing that the timing of visits will vary among participants).
- Time to symptom deterioration (TTSD) will be estimated using the KM product-limit method, by arm as randomized. Two-sided 95% confidence intervals for median TTSD will be computed.

Analyses of patient-reported outcomes will be performed on both the randomized PD-L1 CPS ≥ 20 population and the all randomized population.

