#### 7.9.2 FACT-HN

FACT-HN data will be described by treatment group as randomized in the following ways:

- Scores and post-baseline changes in scores for the following components of the FACT-HN will be summarized at each assessment time point using descriptive statistics (ie, N, mean with SD and 95% CI, median, first and third quartiles, minimum, maximum): FACT-G, PWB, SWB, EWB, FWB, HNC, FHNSI-10, FACT-HN TOI, and FACT-HN total.
- A line graph summarizing the mean changes from baseline will be produced.
- The proportion (N) of subjects with symptomatic deterioration, defined as a clinically meaningful decline in FHNSI-10 score (worsening from baseline ≥ 3 points), will be summarized at each assessment time point.
- TTSD will be estimated using the Kaplan-Meier (KM) product limit method and will be displayed graphically. A table will be produced presenting number of events, number of subjects involved, medians, and 95% CIs for the medians. Median values of TTSD, along with two-sided 95% CI in each treatment group will be computed based on a log-log transformation method.
- The proportion (N) of subjects with symptomatic deterioration, defined as a clinically meaningful decline in FHNSI-10 score (worsening from baseline ≥ 3 points), or death, will be summarized at each assessment time point.
- Time to symptomatic deterioration or death will be estimated using the Kaplan-Meier (KM) product limit method and will be displayed graphically. A table will be produced presenting number of events, number of subjects involved, medians, and 95% CIs for the medians. Median values of time to symptomatic deterioration or death, along with two-sided 95% CI in each treatment group will be computed based on a log-log transformation method.

- Proportion (N) of subjects endorsing each response option for item GP5, "I am bothered by side effects of treatment," will be summarized by treatment group at each assessment time point. Separate analyses will be performed including or excluding cases with missing data.
- Proportion (N) of subjects with post-baseline improvement, stability, or worsening in GP5 item response will be summarized by treatment group at each assessment time point (except baseline). Separate analyses will be performed including or excluding cases with missing data.

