#### 10 DOCUMENT HISTORY

Table 10-1: Document Revision History

Version Number	Author(s)	Description
1.0		Initial release dated 21-Oct-2019
2.0		• Per US FDA feedback, removed the second formal interim analysis (at 90% information fraction).
		• Added to Section 7.9.2 the analysis of time to symptomatic deterioration or death.
		• Corrected a typo in Table 7.4.1-3 replacing number 75 with 100.

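### The SAP's TTSD omits death and has no censoring rule, so the Kaplan-Meier result labelled TTSD is not the endpoint defined in the protocol

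*SAP*

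**What the plan says.** **Protocol.** Section 8.3.3 sets the threshold: "A clinically meaningful decline will be defined as a reduction of FHNSI-10 score ≥ 3 points". It then settles the other two outcomes. On death: "Subjects who die without a reported deterioration will be considered to have deteriorated on the date of their death". On the rest: "Those who neither deteriorate nor die will be censored at the time of their last FHNSI-10 assessment". Section 8.4.6 gives the method: "Time to symptom deterioration (TTSD) will be estimated using the KM product-limit method, by arm as randomized". TTSD in the protocol is thus a composite of decline and death, with a stated censoring rule.

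**SAP.** Section 4.3.7 keeps the name and the 3-point threshold but stops at the decline: "Time to disease-related symptom deterioration (TTSD) is defined as the time from randomization to a clinically meaningful decline from baseline FHNSI-10 score". It does not mention death or censoring. Section 7.9.2 then says: "TTSD will be estimated using the Kaplan-Meier (KM) product limit method and will be displayed graphically". Further down, the same section plans a second curve: "Time to symptomatic deterioration or death will be estimated using the Kaplan-Meier (KM) product limit method and will be displayed graphically". The document history in Section 10 records when that arrived, in version 2.0: "Added to Section 7.9.2 the analysis of time to symptomatic deterioration or death". Section 7.9.2 also lists per-visit proportions of participants with decline, and with decline or death.

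The exploratory objective in SAP 3.3 is worded in terms of TTSD. Section 4.3.7 does not say that it departs from the protocol. By contrast, Section 4.3.1 states openly that PFS2 is not in the protocol.

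**The concern.** One name covers two quantities. A report that follows the SAP will present the decline-only curve as TTSD, and that is the result a reader will set against the TTSD objective. The protocol's own endpoint will appear beside it under a different title, as though it were a supplement.

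The decline-only curve is also hard to interpret. If death is not an event, a participant who dies without a recorded decline can only be censored, at death or earlier. The SAP does not say this, but no other reading fits a KM analysis. The curve then describes decline in a hypothetical setting in which nobody dies first. With a planned control median OS of 10.8 months, many participants will die first. At stake is the correct description of an exploratory patient-reported outcome. The primary and key secondary tests are not affected.

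**Working it through.** Neither document gives an event number, rate or power for TTSD, so there is no planned figure to reproduce. The check compares the definitions and then sizes the difference under stated assumptions.

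**Definitions side by side**

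| Element | Protocol 8.3.3 | SAP 4.3.7, TTSD | SAP 7.9.2, second analysis |
|---|---|---|---|
| Decline of at least 3 points | event | event | event |
| Death without decline | event on date of death | not mentioned | event |
| Neither | censored at last FHNSI-10 | no rule | no rule |

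**Inputs**

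- Median OS on EXTREME: 10.8 months (Protocol Table 8.1-1, SAP Table 5-1). This is the all-randomized value; the outcomes analyses use those with a baseline and at least one later assessment.
- Latent median time to decline *m*: 6, 9, 12 or 18 months. This is an assumption, since the documents give no deterioration rate.
- Times to decline and death are exponential and independent. This is also an assumption.

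**Formulas**, with decline hazard d = ln2/*m* and death hazard x = ln2/10.8 = 0.0642 per month:

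- SAP TTSD, deaths censored: 1 − KM(t) = 1 − exp(−d·t)
- Share who actually decline (cumulative incidence): d/(d+x) × [1 − exp(−(d+x)·t)]
- Protocol composite: 1 − exp(−(d+x)·t), with median ln2/(d+x)

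**Worked case, *m* = 9, t = 12.** d = 0.0770 and d + x = 0.1412.

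- SAP TTSD: 1 − exp(−0.924) = 60.3%
- Composite: 1 − exp(−1.694) = 81.6%
- Cumulative incidence: (0.0770/0.1412) × 0.816 = 44.5%
- Medians: 9 months for the SAP TTSD, and 0.6931/0.1412 = 4.9 months for the composite

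**All assumed medians, EXTREME, 12 months**

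| *m* (also the SAP TTSD median), months | SAP TTSD, 1 − KM | Cumulative incidence of decline | Protocol composite | Composite median, months |
|---|---|---|---|---|
| 6 | 75.0% | 56.8% | 88.4% | 3.9 |
| 9 | 60.3% | 44.5% | 81.6% | 4.9 |
| 12 | 50.0% | 36.4% | 76.9% | 5.7 |
| 18 | 37.0% | 26.6% | 70.8% | 6.8 |

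The SAP TTSD lies between the two quantities a reader might take it for. It is below the protocol composite by 13.4 points (88.4 − 75.0) to 33.8 points (70.8 − 37.0). It is above the cumulative incidence by 10.4 points (37.0 − 26.6) to 18.2 points (75.0 − 56.8).

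Using the planned 13-month median for nivolumab + ipilimumab as a constant hazard, with *m* = 9, gives 60.3%, 46.7% and 79.1%, and a composite median of 5.3 months. The SAP figure is 60.3% in both arms because its formula contains no death term.

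**The case against.** The strongest reply is that nothing is lost. SAP 7.9.2 plans the deterioration-or-death analysis with curve, event count, medians and confidence intervals, so a reader of the report gets both versions. That stands, and it limits the harm. It does not settle which result is TTSD, and neither SAP analysis carries the protocol's censoring rule.

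A second reply is that no planned proportion is overstated. The proportions in 7.9.2 are per-visit counts rather than 1 − KM, and nothing says that 1 − KM will be reported as the share who deteriorate. This also stands. The 10 to 18 points apply only if the curve is read that way.

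Third, a cumulative incidence curve for an exploratory, descriptive endpoint is partly a matter of preference once the composite is reported. That is fair. The protocol conflict is the error, and the competing-risk display is the suitable way to keep a decline-only result.

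A reader might go further and infer that censoring deaths makes nivolumab + ipilimumab look better, because the plan assumes a hazard ratio for death of 1.2 for the first 7 months. The documents do not support that:

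- The calculation assumes independence, so censoring at death is non-informative in it and changing the death hazard leaves the SAP curve unchanged. It cannot show informative censoring. Those who die may well be nearest to decline, but the documents give nothing to quantify it.
- The same assumption has a hazard ratio of 0.55 after month 7. With an exponential control arm, cumulative mortality crosses where 1.2 × 7 + 0.55 × (t − 7) = t, so t = 4.55/0.45 = 10.1 months. By month 12 deaths are about 51% on nivolumab + ipilimumab and 54% on EXTREME.
- Neither document plans a test or a hazard ratio for TTSD. Both specify estimates by arm.

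**Conclusion.** The concern holds in a limited form. SAP 4.3.7 and Protocol 8.3.3 define TTSD differently, the SAP does not flag the change, and the SAP gives no censoring rule. The text alone establishes this, without any modelling.

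The size is illustrative. For EXTREME at 12 months with a 9-month latent median, the result labelled TTSD would be 60% against 82% under the protocol definition, and its median 9 against 4.9 months. Against the protocol endpoint it therefore understates events and lengthens the median. Only when 1 − KM is read as the share who deteriorate is it too high: 60% against 45%, or 10 to 18 points across assumed medians of 6 to 18 months. These figures rest on independent exponential times and assumed decline rates.

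No bias between arms is shown. The per-visit proportions are unaffected. TTSD is exploratory and carries no alpha, so type I error, power and the primary conclusions do not change.

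**What to change.** In SAP 4.3.7, define TTSD as in Protocol 8.3.3: first FHNSI-10 decline of at least 3 points or death, otherwise censored at the last FHNSI-10 assessment. In SAP 7.9.2, identify the planned deterioration-or-death KM analysis as that endpoint and give it the TTSD label and this censoring rule.

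If decline alone is still wanted, give it a different name and replace its KM curve with a cumulative incidence (Aalen-Johansen) estimate by arm, with death as a competing event and its own stated censoring rule.

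The cost is SAP wording and one standard procedure. No new data are needed, and no change to the protocol or to any confirmatory test.

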#### 5 SAMPLE SIZE AND POWER

The primary objectives of this study are to compare OS between treatment groups, in all randomized subjects and randomized subjects with PD-L1 CPS  $\geq$  20. OS will be compared at the 0.025 alpha level for each of the above two populations.

The OS comparison in all randomized subjects will require up to 741 deaths. This number of events ensures that a two-sided, alpha = 0.025 group sequential test using the O'Brien and Fleming spending function and with an interim analysis after approximately 80% of events, will have overall 97% power for a HR of 1.2 for the first 7 months and 0.55 thereafter.

Delayed separation of KM curves is included in the alternative hypotheses for OS because it was observed in CA209141, a randomized phase 3 study of nivolumab versus investigator's choice

therapy in platinum-refractory, recurrent/metastatic SCCHN and in KEYNOTE-048, a randomized phase 3 study of pembrolizumab or pembrolizumab plus chemotherapy versus cetuximab with chemotherapy in untreated recurrent/metastatic SCCHN.

The final analysis of OS in all randomized subjects is projected to occur 51 months after the first patient was randomized. An interim analysis in this population will be performed when approximately 593 deaths occur, or all randomized subjects have been followed up for at least 12 months, whichever is later. It is projected for 39 months after the first patient was randomized.

At the same time as the OS analysis is done for all randomized subjects, OS will also be compared between arms in the randomized subjects with PD-L1 CPS  $\geq$  20 population via a two-sided, alpha = 0.025 group sequential test procedure incorporating the O'Brien and Fleming alpha spending function. The group sequential test would have an interim analysis and the final analysis of OS, at which approximately 298 and 372 deaths, respectively, are expected. With this many events, the test procedure would have an overall 99% power if the HR was 1.06 for the first 7 months and 0.45 thereafter. Table 5-1 summarizes the statistical assumption and power calculation.

Table 5-1: Statistical Assumption and Power Calculation

Primary endpoints	OS for ITT (N = 930)	OS for PD-L1 CPS $\geq$ 20 (N = 465)
Median OS months (N+I/ EXTREME	13/10.8	14.9/10.8
regimen)		
Average hazard ratio	0.74	0.61
Alpha level (IA/FA)	0.01/0.022	0.01/0.022
Event Number (IA/FA)	593/741	298/372
Critical hazard ratio (IA/FA)	0.81/0.845	0.74/0.788
Power (IA/FA)	66%/97%	87%/99%
Estimated time of LPLV (IA/FA)	39/51 months	39/51 months

If comparison of OS in the randomized subjects with PD-L1 CPS  $\geq$  20 is significant, OS in randomized subjects with PD-L1 CPS  $\geq$  1 will be subsequently tested at the same time using group sequential testing procedure. The interim and final analyses of this endpoint are expected to observe approximately 505, and 632 deaths at time of analyses, and the corresponding power is 74%, and 98% respectively with an average hazard ratio of 0.7.

